10.4 PATIENT DISPOSITION

A listing of all patients prematurely discontinued from the study, along with reasons for discontinuation will be provided. In addition, the total number of patients for each of the following categories will be summarized.

- The total number of screened patients: met the inclusion criteria regarding the target indication and signed the informed consent
- The total number of enrolled patients: met all inclusion/exclusion criteria and receive at least one dose of therapy
- The analysis sets (SAF, PP)
- The total number of patients who discontinued the study, and the reasons for discontinuation

• A listing of patients prematurely discontinued from treatment, along with reasons for discontinuation

10.5 STATISTICAL METHODS

All analyses will be summarized using descriptive statistics and data will be presented in tabular format for each treatment group and pooling all bermekimab dose groups together. Continuous data will be summarized for each treatment group using the number of observations available (N), means, standard deviation (SD), minimums, medians, and maximums. Categorical data will be summarized for each treatment group using counts and percentages. Missing data will not be categorized in the summaries.

10.5.1 Handling Missing Data

If baseline assessment is not available, the baseline value will remain missing. The subject will not be included in baseline summaries.

10.5.2 Adjustment for Multiple Comparisons

No adjustment for multiple comparisons will be made.

10.5.3 Demography and Baseline Characteristics

Demographic and baseline characteristics will be summarized descriptively by treatment group. Continuous variables will be summarized with mean, median, SD, minimum, and maximum. Categorical variables will be summarized with frequency and percentage.

10.5.4 Efficacy Analysis

All primary and secondary efficacy analyses will be performed for SAF and PP populations. Summary statistics will be provided to evaluate the overall treatment effect and effect within the treatment group. No statistical comparison of differences will be performed across bermekimab dose groups.

Change from baseline to visit 8 will be summarized using descriptive statistics. Corresponding 95% confidence interval of the point estimate of mean change will be provided by treatment group and for overall pooled population. The number and percent of subjects achieving the response (as specified for the secondary endpoints) will be summarized by treatment groups and overall population along with 95% confidence interval for the point estimate. Number and percent of patients achieving response in EASI, and SCORAD core from baseline at visit 8, will be reported separately, along with 95% confidence interval for 50% or greater reduction.

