- Change in SCORing Atopic Dermatitis (SCORAD) score from baseline to visit 8
- Patients (%) achieving 50% or greater reduction in EASI Score from baseline at visit 8
- Patients (%) achieving 50% or greater reduction in SCORAD Score at visit 8
- Change (%) in Patient Oriented Eczema Measure (POEM) Scores from baseline to visit 8
- Changes in Global Individual Signs Score (GISS) from baseline to visit 8
- Change from baseline to visit 8 in Dermatology Life Quality Index (DLQI)
- Change from baseline to visit 8 in Hospital Anxiety Depression Scale (HADS)

• Change (%) from pre- and post- injection of Visit 1 Questionnaire for pruritus, pain and erythema

Trial Design:

Phase 2, Open label, Dose Escalation Study of Bermekimab (MABp1) in Patients with Moderate to Severe Atopic Dermatitis.

Group A (n=9): patients will receive a total of 4 X 200mg subcutaneous injections of bermekimab. Dosing will occur weekly from visit 1 to visit 4.

Group B (n=20): patients will receive a total of 8 X 400mg subcutaneous injections of bermekimab. Dosing will occur weekly from visit 1 to visit 8.

Inclusion Criteria: No waivers/exemptions will be granted for protocol inclusion/exclusion criteria.

Subjects are included in the study if they meet all of the following criteria:

- Written informed consent provided by the patient
- Age ≥ 18 years
- Chronic Atopic Dermatitis present for at least 3 years
- Disease is not responsive to topical medications, or for whom topical treatments are not indicated or desired
- Willing and able to comply with all clinic visits and study-related procedure
- EASI score ≥ 16 at screening and baseline visits
- IGA score \geq 3 at screening and baseline visits
- $\geq 10\%$ body surface area (BSA) of AD involvement at screening and baseline visits
- Documented recent history (within 6 months before the screening visit) of inadequate response to treatment with topical medications or for whom topical treatments are otherwise medically inadvisable or undesired

Exclusion Criteria:

Subjects with ANY of the following will be excluded from the study:

- Treatment with an investigational drug within 8 weeks of baseline visit
- Having received the following treatments within 4 weeks before the baseline visit, or any condition that, in the opinion of the investigator, is likely to require such treatment(s) during the first 4 weeks of study treatment:

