1.2 RATIONALE

Atopic dermatitis (AD) is an inflammatory skin disease affecting as much as 20% of the population in western industrial societies. Chronic eczema in AD and associated pruritus can be a significant cause of morbidity and impact life quality. Disease pathogenesis is complex but ultimately converges on a pathological inflammatory process that disrupts the protective barrier function of the skin.

The prototypical inflammatory cytokine interleukin-1 alpha (IL-1 α) plays a key role in the pathophysiology of a wide range of inflammatory skin disorders⁸. Bermekimab is a natural human antibody that exhibits immunoregulatory activity through blocking IL-1 α activity. Keratinocytes are a major reservoir of IL-1 α and may be a key source of inflammatory stimulus in AD. IL-1 α is present on leukocytes, where its role in leukocyte trafficking and infiltration may represent a key step in the chronic inflammation of AD. IL-1 α is a key inducer of matrix metalloproteinases activity which could be directly involved in the epithelial barrier breakdown in AD⁹. Loss of regulation of IL-1 results in systemic inflammation with extensive skin involvement¹⁰.

In previous dermatology studies bermekimab was well tolerated and showed impressive therapeutic activity. Dose ranging of the subcutaneous formulation of bermekimab is now being studied in a 6 week open label treatment regimen for AD in order to establish the basis for further randomized studies.

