3. STUDY DESIGN AND OBJECTIVES

Phase 2, open label, dose escalation study of two dose cohorts of bermekimab in patients with moderate to severe atopic dermatitis. The study is multicenter, and will consist of two dose levels: Bermekimab administered subcutaneously at a dose of 200 mg weekly (4 doses) and bermekimab administered subcutaneously at a dose of 400 mg weekly (8 doses). Patients taking the 200mg dose will be followed for 5 weeks (6 visits, day 35 ± 20 , and patients taking the 400mg dose will be followed for 8 weeks (9 visits, day 56 ± 20) to allow for assessment of safety and preliminary efficacy.

Dose escalation details can be found in Section 5.3.

The protocol of the study will be approved by the Institutional Review Board (IRB) or the Ethics Committee (EC) of the participating study sites. Depending on the participating countries, both local and central IRB/EC approvals will be granted. The study will be registered at www.clinicaltrials.gov before the enrollment of the first patient. The trial will be conducted in compliance with the protocol, GCP, and all applicable regulatory requirements.

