- Vital signs (blood pressure, pulse, oxygen saturation, respiratory rate and body temperature)

Bermekimab subcutaneous injection in accordance with injection site determined by BMI at Screening

Post bermekimab subcutaneous injection

- 1 hour monitoring post-injection
 - Injection reaction
 - Vital signs (blood pressure, pulse, oxygen saturation, respiratory rate and body temperature) one hour post injection (70 +/- 10 minutes)
- Adverse event monitoring

Visit 5 (day 28 +/-2)

> At least 45 minutes before injection: When using pre-filled syringes, remove syringe from

refrigeration and lay flat; allow to warm to room temperature. Do not heat

Pre-injection

- Concomitant medications/treatments
- Physical Examination
- o DLQI
- Urine pregnancy
- o EASI
- o IGA
- HADS
- Pruritus/Pain NRS: data from patient diary to be recorded at this time if available
- o SCORAD
- o POEM
- o GISS
- Blood draw:
 - chemistry and hematology, 12.5mL
 - PK and Biomarker Analysis, 6mL
- Vital signs (blood pressure, pulse, oxygen saturation, respiratory rate and body temperature)

Bermekimab subcutaneous injection in accordance with injection site determined by BMI at Screening

Post bermekimab subcutaneous injection

- ➤ 1 hour monitoring post-injection
 - Injection reaction
 - Vital signs (blood pressure, pulse, oxygen saturation, respiratory rate and body temperature) one hour post injection (70 +/- 10 minutes)
- Adverse event monitoring

Visit 6 (day 35 +/-2)

> At least 45 minutes before injection: When using pre-filled syringes, remove syringe from

refrigeration and lay flat; allow to warm to room temperature. Do not heat

Pre-injection

• Concomitant medications/treatments

- o DLQI
- Urine pregnancy
- EASI
- o IGA
- HADS
- Pruritus/Pain NRS: data from patient diary to be recorded at this time if available
- o SCORAD
- POEM
- o GISS
- Vital signs (blood pressure, pulse, oxygen saturation, respiratory rate and body temperature)

Bermekimab subcutaneous injection in accordance with injection site determined by BMI at Screening

Post bermekimab subcutaneous injection

- ➤ 1 hour monitoring post-injection
 - Injection reaction
 - Vital signs (blood pressure, pulse, oxygen saturation, respiratory rate and body temperature) one hour post injection (70 +/- 10 minutes)
- Adverse event monitoring

Visit 7 (day 42 +/-2)

> At least 45 minutes before injection: When using pre-filled syringes, remove syringe from

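### The visit 8 efficacy tables give no interpretable information by dose, and the matched visit 5 data that could are collected but not analysed

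*Combined protocol and SAP*

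**What the plan says.** Section 1.2 states the purpose: "Dose ranging of the subcutaneous formulation of bermekimab is now being studied in a 6 week open label treatment regimen for AD", and this is done "in order to establish the basis for further randomized studies". Section 3 calls the trial a "Phase 2, open label, dose escalation study of two dose cohorts of bermekimab". The primary endpoint is safety and tolerability; efficacy is secondary.

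On efficacy, Section 10.5.4 says "Change from baseline to visit 8 will be summarized using descriptive statistics". It gives 95% intervals for mean change and for response, by group and for the pooled population, and adds that "No statistical comparison of differences will be performed across bermekimab dose groups". Section 10.5 applies the same layout throughout: "data will be presented in tabular format for each treatment group and pooling all bermekimab dose groups together". The one efficacy endpoint not tied to visit 8 is the Visit 1 questionnaire, taken before and after the first injection.

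Two rules make visit 8 decisive. Section 10.3.1 admits to the per-protocol set only patients with both a baseline and a visit 8 assessment. Section 3.1 counts a missing visit 8 IGA as non-response.

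The documents differ on what Group A (9 patients, 200 mg) does:

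- The Synopsis gives it four weekly injections, at visits 1 to 4.
- Section 3 also gives four doses, and follows this group for 5 weeks and 6 visits, ending at day 35.
- The calendar in Section 5.2 shows injections at visits 1 to 8 and assessments to visit 9, with no distinction between groups.

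**The concern.** If the trial is meant to inform the dose for later randomized studies, the useful efficacy information is how patients on 200 mg and on 400 mg fare at the same time after the same number of doses. The plan gives no such figure. Its only by-group efficacy tables after visit 1 are at visit 8, where the two groups are not in a like-for-like state and one of them may have no data.

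A reader would still see the two visit 8 columns next to each other, and a pooled column beside them. If Group A's column is empty, filled with automatic failures, or measured four weeks after its last dose, both the apparent dose difference and the pooled result can mislead. Meanwhile every efficacy scale is recorded at an earlier visit where the groups match on time and number of doses.

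**Working it through.** **The plan's own figure.** The sample size is 29, described in Section 10.2 as one of convenience. The only check available is 9 + 20 = 29, which agrees. No SD, effect size or power is given.

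**Inputs.** Group A n = 9, 200 mg; Group B n = 20, 400 mg (Synopsis). Nominal days: visit 4 = 21, visit 5 = 28, visit 6 = 35, visit 7 = 42, visit 8 = 49, with windows of 2 days either side (Section 5.2). Efficacy scales are scored before injection at each dosing visit (Section 5.1).

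**Visit 8 under each account of Group A.**

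| Account | Group A at visit 8 | Consequence |
|---|---|---|
| Section 3: four doses, last visit is visit 6 (day 35) | Not seen | Cells empty or scored as failures |
| Four doses, but seen to visit 8 | 4 doses; 49 − 21 = 28 days since the last | Group B has had 7 doses and is 49 − 42 = 7 days since the last |
| Section 5.2 calendar read literally | 7 doses, 7 days since the last | Matched, but contradicts four doses in the Synopsis and Section 3 |

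**Size of the problem under Section 3.**

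- Per-protocol set: 0 of 9 from Group A, so the pooled per-protocol result is Group B alone.
- IGA response in the safety set: Group A is 0/9 by rule. The exact 95% upper limit is 1 − 0.025^(1/9) = 33.6%, so the table would show an interval of 0 to 33.6% for patients never assessed.
- Pooled IGA rate = Group B rate × 20/29. Assumed Group B rates of 30%, 50% and 70% would be reported as 20.7%, 34.5% and 48.3%.

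**Visit 5.** Section 5.1 lists EASI, IGA, SCORAD, POEM, GISS, DLQI, HADS and the itch and pain NRS before any injection. Under all three accounts each group has had four weekly doses (4 × 200 = 800 mg and 4 × 400 = 1,600 mg) and is 28 − 21 = 7 days past the fourth. If Group A stops at four doses, visit 5 is the last visit matched on dose number: by visit 6 the count is 4 versus 5.

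**Precision of a visit 5 difference, Group B minus Group A.**

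- Unadjusted 95% half-width: t(0.975, 27) × √(1/9 + 1/20) = 2.052 × 0.4014 = 0.82 SD of the change score.
- With dropout: 0.88 SD at 8 versus 18, and 0.94 SD at 7 versus 16.
- Adjusted for baseline: t(0.975, 26) × 0.4014 × √(1 − r²), where r is the within-group correlation of baseline with change. For assumed r = 0.3, 0.5 and 0.7 this gives 0.79, 0.71 and 0.59 SD, ignoring any small loss from baseline imbalance.
- In EASI points, for an assumed SD of change of 8, 10, 12 or 15 (the documents give none), the unadjusted half-width is 6.6, 8.2, 9.9 or 12.4.

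**The case against.** The strongest defence is that this is an open-label escalation study with safety as its primary endpoint. The cohorts are sequential (Section 5.3 opens Group B after Group A's safety review), the sample is one of convenience, and Section 3 describes the goal as safety and preliminary efficacy. Dose ranging appears in one sentence of the rationale. Declining to test sequential, non-randomized cohorts against each other is ordinary caution. That stands: the defect is the missing description at a shared time point, not the missing test.

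Three stronger readings are tempting, and the documents do not support them.

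- A reader might infer that the trial yields nothing about dose. It does: Section 10.6 summarises safety by dose group, and PK is sampled in both groups.
- A reader might infer that visit 8 would show a false dose difference because Group A's effect fades off drug. That needs Group A to be seen at visit 8 after stopping at visit 4. Section 3 ends its follow-up earlier, and the Section 5.2 calendar shows it still being injected. Nothing in the documents gives a rate of fading, so no size can be attached.
- A reader might infer that visit 5 would settle the dose. It would not. The contrast is 9 versus 20, non-randomized and open label, and Section 2.6 gives the two doses from different formulations (100 and 200 mg/mL). At two-sided 5% (assumed), 80% power would need a true difference of about 1.17 SD.

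Section 10 calls itself the basis for the SAP, so a fuller plan might add visit 5. None is in the documents, and it would start from the text of 10.5.4.

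**Conclusion.** The concern holds for efficacy by dose and goes no further. If Group A receives four doses, as the Synopsis and Section 3 both say, its visit 8 results are either absent (0 of 9 per protocol, 0/9 on IGA by rule, pooled IGA rate cut to 20/29 of Group B's) or mixed with number of doses and time since dosing. Only the literal calendar would make visit 8 comparable, and it conflicts with those two sections.

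Visit 5 is matched on time and number of doses under every account and is already collected. What it can give is an exploratory estimate with a 95% half-width of about 0.82 SD unadjusted. That shows how large a difference remains plausible, but it is no firm basis for choosing a dose. The size in EASI points and the gain from baseline adjustment depend on an SD and a correlation that the documents do not state. The change is worth making because it is cheap and serves the purpose stated in Section 1.2. The primary safety objective is not affected.

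**What to change.** In Section 10.5.4, keep the statement that dose groups will not be formally tested against each other, and add text along these lines:

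> Change from baseline and response at visit 5 will be summarised by dose group with 95% confidence intervals. The Group B minus Group A difference in EASI change at visit 5, adjusted for baseline EASI, will be given with its 95% confidence interval. It is a descriptive, exploratory estimate from sequential, non-randomized cohorts that received different formulations.

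Also:

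- State that by-group visit 8 results are not a dose comparison, and do not pool the groups at visit 8.
- Do not count Group A patients as visit 8 non-responders if no visit 8 is scheduled for them. State how missing scores are handled for response at visit 5, because the Section 3.1 rule is tied to visit 8.
- Reconcile the Synopsis, Section 3 and the Section 5.2 calendar on Group A's injections and follow-up. The 6-week regimen in Section 1.2 and the 7-week treatment period in the Synopsis need the same check.

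The cost is a wording change and one or two extra tables, with no new visits, samples or patients. The downside is a wide, non-randomized estimate that must carry the exploratory label wherever it is reported.

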10.3 ANALYSIS SETS

10.3.1 Safety Analysis Sets

The safety analysis set (SAF) consists of all patients that receive at least one dose of study medication and will be analyzed as treated.

The secondary endpoints will be analyzed based upon the SAF, as well as the per protocol population (PP). The per protocol population will consist of those patients that complete both the baseline and visit 8 assessments of their atopic disease (as specified for the secondary endpoints).

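### For the eight change-from-baseline endpoints the SAF summary is in effect the PP (completer) summary, so it cannot show sensitivity to patients who have no visit 8 score

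*Combined protocol and SAP*

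**What the plan says.** - **Sets (10.3.1).** "The safety analysis set (SAF) consists of all patients that receive at least one dose of study medication and will be analyzed as treated". The PP population "will consist of those patients that complete both the baseline and visit 8 assessments of their atopic disease". Section 10.5.4 adds: "All primary and secondary efficacy analyses will be performed for SAF and PP populations".
- **Method (10.5.4).** "Change from baseline to visit 8 will be summarized using descriptive statistics". A 95% CI for the mean change is given by group and pooled. No longitudinal model is planned.
- **Denominator (10.5).** "Continuous data will be summarized for each treatment group using the number of observations available (N"), and missing values are not shown as a category.
- **Missing data (10.5.1).** "If baseline assessment is not available, the baseline value will remain missing". The section drops such patients from baseline summaries and says nothing about a missing visit 8 value.
- **Exception (3.1).** For IGA 0/1, a missing visit 8 score counts as non-response.
- **Rescue (5.4).** Rescued patients are treatment failures for efficacy, but no value is assigned to their change scores.
- **Data collected (5.1, 5.2).** EASI, SCORAD, NRS, POEM, GISS, DLQI and HADS are recorded at every visit from 1 to 9.
- **Group A (3).** Follow-up is six visits, to day 35.

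**The concern.** Two analysis sets are normally specified so that a reader can compare an all-treated result with a completer result and judge whether withdrawal matters. Here the comparison is empty for the change scores. Both tables would show the same mean and CI, and the one labelled SAF would read as an all-treated estimate.

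This matters if the patients without a visit 8 score did worse than the rest. Section 5.5 stops therapy for clinical progression when the investigator judges that continuing is not in the patient's interest, and Section 5.4 stops it for systemic rescue. The calendar shows no early-termination visit, so nothing in the plan secures a visit 8 score once treatment stops. Section 1.2 says the study is to form the basis for randomized trials, so an inflated mean change could carry into their design.

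**Working it through.** **Plan's own figures.** Section 10.2 describes a convenience sample with no calculation. The only figure to reproduce is the total: 9 + 20 = 29, which agrees. The documents give no SD, expected change or withdrawal rate, so all inputs in steps 3 and 4 are assumptions.

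**1. Endpoints affected.** EASI, percent change in peak weekly averaged NRS, change in weekly averaged peak NRS, SCORAD, POEM, GISS, DLQI and HADS: 8. The Visit 1 questionnaire is a same-day comparison and is not among them.

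**2. Who contributes.**

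| Dosed patient | Change computable | Enters SAF summary | Enters PP summary |
|---|---|---|---|
| Baseline and visit 8 scored | yes | yes | yes |
| Stops drug, attends visit 8 | yes | yes | yes |
| No visit 8 score | no | no | no |

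With w patients missing, n − w contribute in both sets. In Group B with w = 4, that is 20 − 4 = 16 in each. If PP requires every scale to be complete, PP may be smaller by the odd missed questionnaire. The last row does not change.

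**3. Size by arithmetic.** Error of the observed-case mean = (w/n) × (mean change in the missing − mean change in completers). Assume n = 20, completers −15 on EASI, and missing patients between −6 and 0.

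| w | Reported, SAF and PP | Error, points | All-treated mean | Overstated by |
|---|---|---|---|---|
| 0 | −15.0 | 0 | −15.0 | 0% |
| 2 | −15.0 | 0.1 × 9 to 15 = 0.9 to 1.5 | −14.1 to −13.5 | 6% to 11% |
| 4 | −15.0 | 0.2 × 9 to 15 = 1.8 to 3.0 | −13.2 to −12.0 | 14% to 25% |
| 6 | −15.0 | 0.3 × 9 to 15 = 2.7 to 4.5 | −12.3 to −10.5 | 22% to 43% |

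**4. Size by simulation.** Assume Group B, true mean change −14 at visit 8, trajectory SD 9 and residual SD 4, with withdrawal after visits 4 to 7 more likely when the last change was worse than −4. The rows differ in the assumed withdrawal probabilities (120 to 300 runs each). The reference is the full-data mean where available, otherwise the true −14.

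| Withdrawn | Observed-case mean | Reference | Overstated by | 95% CI coverage | Mixed model |
|---|---|---|---|---|---|
| 8% | −14.8 | −14 | 6% | 96% | – |
| 19% | −15.1 | −14 | 8% | 93% | – |
| 19% | −15.62 | −14.03 | 11% | – | −14.00 |
| 20% | −16.1 | −14.1 | 14% | 85% | −14.2 |
| 27% | −17.1 | −14.2 | 20% | 78% | −14.2 |
| 34% | −17.31 | −14.03 | 23% | – | −14.00 |

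In a deliberately extreme case (true mean −12, SD 10, n = 20, 20,000 trials) the worst 2, 4 or 6 responders always leave. The error is 1.8, 3.3 or 4.8 points and coverage falls to 84%, 62% or 39%. When the same numbers leave at random, the error is zero.

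**5. Group A.** Six visits means no visit 8. Read literally, 0 of 9 patients have the endpoint, and the pooled summary can hold at most 20/29 = 69%.

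**The case against.** The strongest reply is that the study is uncontrolled, its primary endpoint is safety, no hypothesis test is planned for that endpoint, and observed-case description is ordinary for such a trial. Each summary reports N, and Section 10.4 lists discontinuations with reasons, so attrition can be seen. This limits the weight of the point. It does not remove it, because the plan still promises two estimates with CIs and delivers one.

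A reader might infer that the stopping rules make missingness depend on outcome. The documents do not establish that. Sections 5.4 and 5.5 stop treatment, not attendance, and Section 10.4 counts study and treatment discontinuation separately. The grade 2 trigger in 5.5 excludes worsening AD, and progression counts only through the investigator's judgement. Outcome-dependent missingness is possible, not shown.

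Objections to the mixed model also stand in part:
- The main simulations make withdrawal depend on observed scores, the condition under which the model is valid, so its recovery of −14 is built in. When withdrawal depended on the next, unseen score (25% withdrawn), the model gave about −14.9, some 6% too favourable (0.9/14).
- Convergence warnings were common at n = 20.
- Used on all weekly scores without a rescue rule, the model would credit post-rescue improvement to the drug.
- A visit 8 mean cannot be estimated for a group with no visit 8.

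**Conclusion.** The point holds for the eight change scores. Under the available-observations rule the SAF summary is essentially the PP summary, and patients without a visit 8 score enter neither. This follows from the stated rules together with the plan's silence on a missing visit 8 value; it needs no simulation.

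The direction of any error is conditional: too favourable if poor responders miss visit 8, zero if nobody does or if they do so at random. Its size rests wholly on assumed inputs. For Group B it is roughly 5% to 25% in most of the scenarios above, and up to 43% if 6 of 20 are missing with no improvement at all. At 8% missing, CI coverage was not harmed.

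Two stronger readings are not supported. No figure for overstatement can be attributed to this trial. Nor is it true that every efficacy analysis leaves withdrawals out: IGA 0/1 counts a missing visit 8 score as non-response, and a patient who stops drug but attends visit 8 is in both sets. The primary safety endpoint is untouched. The gap should be closed, but it does not undermine the study.

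**What to change.** Reconcile Group A's six-visit schedule (Section 3) with the visit 8 endpoints first. Until then, claim no visit 8 model mean for Group A or the pooled population. Then, in Section 10.5.4:

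1. For the SAF in Group B, estimate mean change at visit 8 with a repeated-measures mixed model on the weekly scores from visits 2 to 8. Use visit as a factor, baseline as a covariate and a parsimonious covariance such as autoregressive. Report the 95% CI and state the missing-at-random assumption.
2. Carry the Section 5.4 treatment-failure rule over to change scores, so that scores after rescue do not count as drug effect.
3. Add a sensitivity analysis that sets change to zero for patients who were rescued or have no visit 8 score. With completers at −15, no rescue, and 2, 4 or 6 of 20 missing, it would report −13.5, −12.0 or −10.5. Unlike the present SAF summary, it responds to missingness.
4. Report the number missing at visit 8 by group.
5. Keep the observed-case summary as the PP analysis.

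The cost is SAP wording and modest programming. The scores are already collected, and Section 10 allows the SAP to be revised. The downsides are an untestable missing-at-random assumption and possible model instability at n = 20, which the zero-change analysis helps a reader to judge.
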